7.3.3.1 Adverse Events

An **adverse event or adverse experience (AE)** is any untoward medical occurrence in a patient or clinical investigation patient administered a pharmaceutical product and which does not necessarily have to have a causal relationship with this treatment.

An adverse event (AE) can therefore be any unfavorable and unintended sign (including an abnormal laboratory finding), symptom, or disease temporally associated with the use of a medical product, whether or not considered related to the medical product.

Existing concomitant diseases are not considered AEs, except if they have worsened/adversely progressed during the study.

The Medical Dictionary for Regulatory Activities (MedDRA, Version 22.1 or higher) is used for coding adverse events.

All AEs with start date/time prior to first intake of IMP are pre-treatment AEs and will be assigned to screening.

Any adverse events with missing start date/time or the end date/time are treated as follows:

- If the date is known but the time is unknown, the time will be imputed with a time 0:00 h for the start and with 23:59 for the end. In the listings the unknown time will be displayed as NK. If the start date is a treatment date, then the AE will be assigned to the treatment of that date.
- If the start date is incomplete:
 - Missing day: will be imputed with the 1st of the month unless month is the same month of first dose of study drug; then it will be imputed with first dose date
 - Missing day and month: will be imputed with 1st January unless year is the same as first dose date; then it will be imputed with first dose date
 - Completely missing: impute first dose date unless the end date suggests it could have started prior to this in which case the 1st January of the same year will be imputed as the start date
- If the end date is incomplete:
 - Missing day: will be imputed with the last day of the month unless month is same as month of first dose of study drug; then it will be imputed with the last dose date
 - Missing day and month: will be imputed with 31st December unless year is the same as first dose date; then it will be imputed with last dose date
 - Completely missing (and not ONGOING): if the AE started prior to 1st dose date then it will be imputed the 1st dose date. If the AE started after 1st dose date then it will be imputed with the last dose date

The pre-treatment adverse events which occurred before intake of the first dose of IMP (between screening visit (Visit 1) on Day -1 and Visit 2 on Day 1) will be presented in listings.

The adverse events will be analyzed by means of frequency tables. For an overview a frequency table with numbers of patients affected will be presented by treatment for the categories (Summary of adverse events): total, adverse events leading to discontinuation, serious adverse events, and (serious) adverse events with outcome death.

Further frequency tables will be classified by system organ class (SOC), preferred term (PT) derived from MedDRA and by treatment. The numbers of adverse events as well as the numbers of patients affected will be presented.

Moreover, tables for incidences of adverse events and patients with respect to the following parameters will be created:

- Severity (mild, moderate, severe),
- Relationship between study medication and adverse event (suspected, not suspected),
- Outcome (not recovered / not resolved / unchanged; recovered / resolved, improving/ recovering/ resolving; recovered with sequelae; fatal; condition deteriorating; unknown).

All adverse events will be listed, these listings will be split into three parts containing the following columns:

Part I: Rnd. No. , Report No., Observed AE (in verbatim), Seriousness, Action taken with IMP; Severity, Outcome, Relationship to IMP, Relationship to NIMP

The report number is an identifier for the single adverse events within one patient (chronologically).

This part I will be displayed in two versions:

- first version is sorted by treatment group (where pre-treatment adverse events will be pooled as additional group), random number and report number,
- in the second version the adverse events are sorted by random number and report number.

The second and third part will only be displayed sorted by random number and report number with the following information:

Part II: Rnd. No., Report No., MedDRA Coding: Preferred Term (with Code), Date/Time of onset, Date/Time of end, Last date/time of dose before onset, Last treatment.

Part III: Rnd. No, Report No, Event treatment, Specification of event treatment.

These adverse events will be listed for the safety set. If patients experience adverse events who were not randomized, or had no intake of IMP then further listing for these events will be displayed.

7.3.3.2 Serious Adverse Events

A serious adverse event (SAE) or serious adverse reaction (SAR) is any untoward medical occurrence that at any dose:

- results in death,
- is life-threatening,
- requires inpatient hospitalization or prolongation of existing inpatient hospitalization,
- results in persistent or significant disability/incapacity,
- is a congenital anomaly/birth defect, or
- is medically significant: Medical and scientific judgment should be exercised in deciding whether expedited reporting is appropriate in other situations, such as important medical events that may not be immediately life-threatening or result in death or hospitalization but may jeopardize the subject (patient) or may require intervention to prevent one of the other outcomes listed above.

The serious adverse events will be presented in listings.

7.3.3.3 Assessment of Tolerability

The tolerability will be assessed by the investigator and by the patient at Visit 4 and Visit 6. It is rated using a five-point rating scale: ① = very poor, ② = poor, ③ = medium, ④ = good, ⑤ = very good.

The assessments will be listed by patient.

The results will be presented by means of frequency tables by visit and treatment.

7.3.3.4 Vital Signs

The following vital sign measurements will be obtained according to the schedule of assessments in chapter 9 of the Trial Protocol on each visit and evaluated as normal or abnormal and judged regarding clinical relevance

- Blood pressure, systolic and diastolic [mmHg]
- Pulse rate [beats/min]
- Body temperature [°C]

The vital signs will be listed by patient.

A separate listing for only abnormal results including the assessment of clinical relevance will be presented.

Descriptive statistics for the values and for individual changes (absolute changes) to the baseline (measurement from screening visit) will be presented by measuring time point, parameter and treatment.

7.3.3.5 Physical Examination

A physical examination is performed at the entry and final examination per body system (general state; nutritional state; skin; head, neck; eyes; cardiovascular; respiratory; gastrointestinal; hepatic, biliary; endocrine, metabolic; lymph nodes; urogenital; neurological; psychiatric; musculoskeletal)

The findings, if any, will be listed by patient, abnormal findings will be listed separately.

The results for the examination by body system (normal, abnormal) and for the changes from entry to final will be presented by means of frequency tables. The changes will be displayed as shift for Visit 6 against Visit 1.

7.3.3.6 Examination of Nose, Ears, Mouth / Throat (ENT)

An examination of Nose (septum, mucosa, secretion, obstruction, polyps), Ears (effusion and erythema) and Mouth/Throat (anterior and posterior discharge, dental abnormalities and halitosis) will be performed at screening (Visit 1), at Visit 4 and at Visit 6.

The results will be listed by patient. The results per item and the findings (normal/abnormal) per system will be presented by means of frequency tables. The changes will be displayed as shift tables for Visit 4 against Visit 1 and for Visit 6 against Visit 1.

7.3.3.7 Safety Laboratory Examination

The safety laboratory examination will be performed at Visit 1 (screening) and Visit 6 (end of treatment) for the following:

Hematology: hemoglobin, hematocrit, leukocytes with differential count, erythrocytes, erythrocyte sedimentation rate, MCV, MCH, MCHC, and platelet count

Blood chemistry:

Electrolytes	sodium, potassium, serum calcium, serum albumin, chloride
Substrates	creatinine, total protein, total bilirubin, blood glucose, urea, uric acid
Enzymes	ALT, AST, γ -GT, ALP

The individual values of the clinical laboratory tests (hematology, blood chemistry) will be listed by patient.

Out-of-range values are marked with an assessment of clinical relevance (NCR = not clinically relevant, CR = clinically relevant). The course of out-of-range values is listed separately.

Descriptive statistics for each parameter will be presented by visit and treatment. Further descriptive statistics for individual changes (from Visit 1 to Visit 6) will be presented by treatment.

Frequency tables for the assessment of clinical relevance (normal, abnormal NCR, abnormal CR) will be presented by treatment. The changes of the assessment will be displayed as shift tables from Visit 1 to Visit 6.

In addition, a serum pregnancy test in all female patients is performed at Visit 1 and Visit 6. The results will be listed by patient.

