8.3 Benefit-Risk Evaluation

8.3.1 Adverse Drug Reactions Described in the SmPC of Acetylcysteine 600 mg effervescent tablet

Data from the Summary of Product Characteristic (SmPC)¹⁵

The evaluation of undesirable effects is based on the following information on frequencies:

Very common ($\geq 1/10$)

Common ($\geq 1/100$ to $< 1/10$)

Uncommon ($\geq 1/1,000$ to $< 1/100$)

Rare ($\geq 1/10,000$ to $< 1/1,000$)

Very rare ($< 1/10,000$)

Not known (cannot be estimated from the available data).

Immune system disorders	Uncommon Very rare	Hypersensitivity reactions Anaphylactic shock, anaphylactic / anaphylactoid reactions
Nervous system Disorders	Uncommon	Headache
Cardiac disorders	Uncommon	Tachycardia
Vascular disorders	Uncommon Very rare	Hypotension Hemorrhage
Respiratory, thoracic and mediastinal disorders tract	Rare	Dyspnea, bronchospasm – predominantly in patients with hyperreactive bronchial system in case of bronchial asthma
Gastrointestinal disorders	Uncommon Rare	Stomatitis, abdominal pain, nausea, vomiting, and Diarrhoea Dyspepsia
Skin and subcutaneous tissue disorders	Uncommon	Urticaria, rash, angioedema, itching, exanthema
Ear and labyrinth disorders	Uncommon	Tinnitus
General disorders and administration site conditions	Uncommon Not known	Fever Facial enema

A very rare occurrence of serious skin reactions such as Stevens-Johnson syndrome and toxic epidermal necrolysis have been reported in temporal association with the use of acetylcysteine. In most of these cases reported at least one other drug was administered at the same time, which may have possibly enhanced the described mucocutaneous effects.

In case of recurrence skin and mucosal lesions, medical advice should be sought at once and the use of acetylcysteine terminated immediately.

In addition, the occurrence of hemorrhages in association with the administration of acetylcysteine has very rarely been reported, partially with hypersensitivity reactions. A decreased blood platelet aggregation in the presence of acetylcysteine has been confirmed by various studies. The clinical relevance has not yet been clarified to date.

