- check of inclusion criteria according to protocol
- check of exclusion criteria according to protocol
- investigator's decision on patient's enrolment.

The **blood specimen (30 mL) for the screening safety laboratory investigations** will include the following parameters:

Hematology: hemoglobin, hematocrit, leukocytes with differential count, erythrocytes, erythrocyte sedimentation rate, MCV, MCH, MCHC, and platelet count

Blood chemistry:

Electrolytes sodium, potassium, serum calcium, serum albumin, chloride

Substrates creatinine, total protein, total bilirubin, blood glucose, urea, uric acid

Enzymes ALT, AST, γ -GT, ALP

The investigator will be provided with the original laboratory print-out(s) or certified copy (dated and signed by the laboratory staff) of the original laboratory print-out(s) for the individual patient health medical record file. The laboratory results have to be entered into the CRF. Any values out of range have to be assessed by the investigator as "not clinically relevant" (NCR) or "clinically relevant" (CR). For implausible laboratory values e.g. due to technical error or print-out error, the investigator will use the assessment "implausible value" (IPV).

If medically required, a separate blood draw will be taken for follow-up of CR or IPV parameters.

Serum pregnancy test (hCG) in all female patients. The result will be documented in the CRF. In case of a positive test result, this patient cannot be included in the trial.

All laboratory blood tests will be carried out in a certified local laboratory. A signed and dated list of the normal ranges and units of the laboratory blood and parameters and the certificate of the laboratory will be provided to [REDACTED] before the start of the trial. Also updates of the laboratory reference ranges/ certificates (if any) will be provided to [REDACTED].

VISIT 2 (Day 1 – between 7 and 9 a.m.)

The following procedures will be performed and documented in on this day:

- date and time of examination
- patient identification by means of national ID card or other national ID document
- vital signs measurements of body temperature with documentation of the measuring method used, pulse rate, and blood pressure after 5 minutes rest in sitting position
- documentation of any changes in the concomitant therapy(ies)/ medication(s) or use of other therapeutic measures/ actions
- adverse event questioning
- check of exclusion/withdrawal criteria and further patient eligibility

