
14.3 Safety
	
Vital signs - Descriptive statistics by treatment and visit, safety set
 
Vital signs - Descriptive statistics of individual changes to baseline by treatment and visit, safety set
 
Findings in the physical examination by treatment and visit, safety set
 
Examination of ENT by treatment and visit, safety set
 
Safety laboratory, hematology -Descriptive statistics by treatment and visit, safety set
 
Safety Laboratory, hematology- Value classification by treatment and visit, safety set
 
Safety laboratory, hematology - Changes in the value classification (entry to final) by treatment, safety set
 
Safety laboratory, blood chemistry - Descriptive statistics by treatment and visit, safety set
 
Safety laboratory, blood chemistry - Value classification by treatment and visit, safety set
 
Safety laboratory, blood chemistry - Changes in the value classification (entry to final) by treatment, safety set

14.3.1 Adverse Events (per treatment / per patient)
	
Summary of adverse events, safety set
 
Listing of pre-treatment adverse events, safety set
 
Listing of serious adverse events, safety set
 
Numbers of patients with adverse events by SOC, PT and treatment, safety set
 
Incidence of adverse events by SOC, PT and treatment, safety set
 
Numbers of patients with adverse events by SOC, PT, treatment and severity, safety set
 
Incidence of adverse events by SOC, PT, treatment and severity, safety set
 
Numbers of patients with adverse events by SOC, PT, treatment and causality, safety set
 
Incidence of treatment events by SOC, PT, treatment and causality, safety set
 
Numbers of patients with adverse events by SOC, PT, treatment and outcome, safety set
 
Incidence of adverse events by SOC, PT, treatment and outcome, safety set

14.3.2 Abnormalities in Vital Signs, Laboratory, Physical Examination, etc.	Abnormalities in vital signs, safety set Abnormalities in physical Examination, safety set Abnormalities in ENT examination, safety set Time course of laboratory test results out of reference range, blood chemistry, safety set Time course of laboratory test results out of reference range, hematology, safety set
--	--

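### The laboratory frequency and shift tables merge above-range with below-range values, so no laboratory table counts patients by direction and dose; a low/within/high split would be a cheap improvement.

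*SAP*

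**What the plan says.** SAP 7.3.3.7 plans two sets of categorical laboratory tables. On the first: "Frequency tables for the assessment of clinical relevance (normal, abnormal NCR, abnormal CR) will be presented by treatment". On the second: "The changes of the assessment will be displayed as shift tables from Visit 1 to Visit 6". The assessment in question is the investigator's grading of an out-of-range value as not clinically relevant (NCR) or clinically relevant (CR). It records importance, not whether the value was too high or too low.

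The table list in SAP 8.1, section 14.3, uses titles such as "Safety laboratory, hematology - Changes in the value classification (entry to final) by treatment, safety set", with a matching title for blood chemistry. None mentions direction. Protocol 10.4 asks for a frequency table of abnormal values and does not mention direction either.

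The same SAP section also plans summaries of the measured values: "Descriptive statistics for each parameter will be presented by visit and treatment" and "Further descriptive statistics for individual changes (from Visit 1 to Visit 6) will be presented by treatment". It adds listings of all individual values and a separate listing of the course of out-of-range values.

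**The concern.** Clinically relevant laboratory change is a named safety endpoint (Protocol 10.2.3, SAP 6.3), and the secondary objective is the safety of three doses against placebo. For a parameter with two meaningful tails, a value below range and a value above range are different safety signals. A table that counts both as abnormal cannot show them separately. Two arms with the same number of abnormal results may differ in which tail those results lie in, and a new abnormality in the shift table may be a new low or a new high.

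**Working it through.** The SAP gives no figure to reproduce here. The first step compares the texts; the rest is an illustration on assumed inputs.

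**1. What the tables can distinguish.** Three classes (normal, NCR, CR) give a 3 × 3 shift table.

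| Change from Visit 1 to Visit 6 | Where it appears |
|---|---|
| Normal to low, normal to high | Same cell if the relevance grade is the same |
| High to normal, low to normal | Same cell if the relevance grade is the same |
| High to low, same relevance grade | Diagonal, reads as no shift |
| High to low, grade changes (NCR to CR or the reverse) | Off the diagonal, visible as a shift, direction not shown |

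So a crossing is hidden only within one relevance grade. Each arm's abnormal count is the sum of its highs and its lows.

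**2. Extreme case.** If 10% of one arm were low and 10% of placebo were high, with no other abnormal values, the table would show 10% against 10%. This is constructed to show the mechanism; nothing in the documents says that it will occur.

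**3. Uniform shift.** Assumptions, none from the documents: a standardised normal parameter, reference limits at ±1.96 SD (2.5% in each tail), and visit-to-visit correlation ρ = 0.7. The 225 per group is from SAP 5.4. For an upward shift of d SD on active:

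- high = 225 × [1 − Φ(1.96 − d)]
- low = 225 × Φ(−1.96 − d)

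With no effect each tail holds 225 × 0.025 = 5.6 patients, 11.3 in all. For d = 0.3: high = 225 × 0.0485 = 10.9, low = 225 × 0.0119 = 2.7, merged = 13.6. The high count rises by 5.3, the low count falls by 2.9, and the merged count rises by 2.3 (differences taken before rounding). The offset is partial.

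The chance of a nominal two-sided 5% result in the right direction serves as a yardstick only, since these tables are descriptive. For counts it is Φ{(|p₂ − p₁| − 1.96·√[2p̄(1 − p̄)/225]) / √[(p₁(1 − p₁) + p₂(1 − p₂))/225]}. For mean change it is Φ{d/√[2·2(1 − ρ)/225] − 1.96}.

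| Shift d | High | Low | Merged | Merged table | High-only count | Mean individual change |
|---|---|---|---|---|---|---|
| 0.2 SD | 8.8 | 3.5 | 12.3 | 4% | 13% | 78% |
| 0.3 SD | 10.9 | 2.7 | 13.6 | 7% | 26% | 98% |
| 0.5 SD | 16.2 | 1.6 | 17.8 | 24% | 64% | about 100% |

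At d = 0.3 the mean-change figure is 89% for ρ = 0.5 and about 100% for ρ = 0.9.

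**4. Rises in some patients, falls in others.** If half of an arm moves up by 0.5 SD and half moves down by 0.5 SD, the merged count is 17.8 against 11.3. Here highs and lows add.

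**5. A marked fall in a few patients.** Suppose 10 of 225 on active fall by k SD and the rest are unchanged. The mean moves by 10k/225, which is 0.133 SD for k = 3. Lows = 215 × 0.025 + 10 × Φ(−1.96 + 3) = 5.4 + 8.5 = 13.9; highs = 5.4; merged = 19.3. The spread among patients adds (10/225)(215/225)k² to the variance of change on active, so mean change has Φ{(10k/225)/√[(4(1 − ρ) + (10/225)(215/225)k²)/225] − 1.96}.

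| k | Merged table | Low-only count | Mean individual change, ρ = 0.7 (0.5 to 0.9) |
|---|---|---|---|
| 2 | 15% | 24% | 21% (15% to 42%) |
| 3 | 32% | 48% | 36% (25% to 62%) |
| 4 | 40% | 57% | 49% (37% to 73%) |

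In this situation the mean has no clear advantage over a directional count, and a directional count does better than the merged one.

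**6. High-to-low crossings.** In a simulation with ρ = 0.7 and shifts of 0, 0.3 and 0.5 SD, crossings from one tail to the other were practically absent (0.0 per 225).

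**The case against.** The strongest case against is that direction is already available elsewhere.

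- Values and within-patient changes are summarised by treatment with mean, SD, median, minimum and maximum (SAP 7.2.1, 7.3.3.7). For a systematic shift these are far more sensitive than any count, as the uniform-shift table shows. Within-patient changes also remove constant offsets between laboratories.
- Under Protocol 9.3.4 a laboratory value judged clinically relevant is an adverse event, and SAP 7.3.3.1 tabulates those by preferred term and treatment. Where the coded term names the direction, patients are counted by direction and dose.
- SAP 8.1, section 14.3.2, lists the time course of out-of-range results.

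All of this stands, and it limits the point to two sets of descriptive tables. It does not remove the point. Means can miss marked changes in a few patients. They also pool local laboratories from approximately 40 centers. SAP 8.1 names a table of individual changes for vital signs but none for laboratory data, although SAP 7.3.3.7 promises the summary. The adverse event route covers only values reported as events, and the listings would have to be counted by hand.

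A reader might infer that opposite drug effects cancel in these tables. As a general statement that is wrong: within an arm, highs and lows add, and only more highs with fewer lows offset, incompletely. A reader might also infer that every high-to-low change is hidden. That holds only within one relevance grade, and such crossings are probably rare. Nor does the remark in Protocol 8.3.1 that "the occurrence of hemorrhages in association with the administration of acetylcysteine has very rarely been reported" point to low platelet counts: the text goes on to platelet aggregation.

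**Conclusion.** The point holds as a limited one. The frequency and shift tables carry no direction, and no planned laboratory table counts patients below range separately from patients above range by treatment group. For two-sided parameters this can mask a directional difference between a dose and placebo.

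It would go too far to conclude that the planned analysis cannot show a rise in low platelets, low leukocytes or high liver enzymes. It would not show them as separate counts in the laboratory tables, but other planned outputs keep direction.

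How much is masked cannot be derived from the documents. The illustration rests on a normal distribution, a 95% reference range, the chosen shifts and the visit-to-visit correlation, all of them assumptions. Values already out of range at entry because of the acute illness would alter the counts; the documents give no such data. The primary and other efficacy analyses are unaffected.

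**What to change.** In SAP 7.3.3.7 and the section 14.3 tables of SAP 8.1, class each value as below, within or above the local reference range and cross this with NCR/CR. That gives five levels: low CR, low NCR, normal, high NCR, high CR. Build the frequency tables and the Visit 1 to Visit 6 shift tables on these levels, by treatment. Counts by multiples of the local upper limit for ALT, AST, γ-GT and ALP are an optional addition.

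The cost is programming and no new patient data. Results are entered in the CRF, and Protocol section 9 (Visit 1) requires this to be supplied before the trial starts: "A signed and dated list of the normal ranges and units of the laboratory blood and parameters". The documents do not say that the ranges are held as database fields; if they are not, they must be entered. The change should be made before unblinding.
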